The **P**otassium Intake-response **T**rial to **C**ontrol **H**ypertension (**PITCH**) will test the intake-response relationship between potassium supplementation and BP, which may (1) inform clinical guidelines on the optimal level of potassium supplementation for BP lowering among adults with elevated BP and hypertension and dietary guidelines for population intake and (2) lay the foundation for further investigations, including mechanistic studies and outcome trials. A large meta-analysis of RCTs identified a dose-response relationship between BP lowering and risk of CVD, with a 5 mm Hg reduction in systolic BP reducing major CVD events by 10%.⁸ Modeling studies suggest that as little as a one mm Hg reduction in the mean systolic BP in the US population would reduce >20,000 coronary heart disease, stroke, and heart failure events annually.^{30,31}

Our long-term goal is to establish effective, scalable, and sustainable nonpharmacological

interventions, like potassium supplementation, for primary prevention of CVD. The specific goal of PITCH is to study the intake-response effect for 4 levels of potassium supplementation on 24-hour systolic BP among adults with untreated elevated BP or hypertension. We will test the following hypotheses:

Primary hypothesis: Compared with placebo (0 mmol/day potassium supplementation), there is a progressive, linear dose-response relationship between increasing doses of oral potassium supplementation (30, 60, and 90 mmol/day or 1173, 2346, 3519 mg/day) and decreasing levels of 24-hour systolic BP from baseline to 12-weeks of follow-up, and the largest BP lowering effect will be observed with a dose of 90 mmol/day (3519 mg/day).

Secondary hypotheses: Potassium supplementation improves levels of 24-hour diastolic BP, and office, daytime, and nighttime systolic and diastolic BP, and these improvements are greater with increasing potassium intake.

Exploratory hypotheses: We will examine the effects of potassium supplementation on other CVD risk factors, such as sodium excretion, and study the mediating effects of potassium-induced changes in CVD risk factors on BP. In addition, we will explore treatment effects by subgroups, including age, sex, race, baseline BP, central adiposity, and baseline sodium and potassium intake.

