Using a parallel arm trial design and a stratified, blocked randomization scheme, participants will be assigned to placebo or 1 of 3 active intervention arms. Assuming 85% follow-up, the trial will provide 90% power to detect an intake-response relationship based on a net 24-hour systolic BP reduction of 1.5 mm for each additional 30 mmol/day (1173 mg/day) of supplemental potassium intake during 12 weeks of treatment, with a significance level of 0.05. The net effects of BP reduction will be calculated as mean changes in BP from baseline in the potassium supplementation groups minus mean change in BP in the placebo group. To achieve these study aims, we will:

- Recruit 224 adults (n=56 in each group) with elevated BP or hypertension (defined as average untreated office systolic BP 120-159 mm Hg and diastolic BP <100 mm Hg).
- Randomize participants to placebo or 1 of 3 potassium supplementation arms in which 30, 60, or 90 mmol/day (1173, 2346, or 3519 mg/day) of additional oral potassium will be administered for 12 weeks.
- Measure BP, urinary excretion of sodium and potassium, and safety parameters in all participants at baseline, 6 weeks, and 12 weeks, using trained and certified study staff who are blinded to the participants' study assignment.
- Examine net differences in 24-hour systolic BP (primary outcome), 24-hour diastolic BP, and office, daytime, and nighttime systolic and diastolic BP, from baseline to 12 weeks of follow-up between the 4 groups per intention-to-treat analysis.
- Examine the effects of potassium supplementation on other CVD risk factors and explore mediating and modifying effects by CVD risk factors, including age, sex, race, baseline BP, central adiposity, baseline sodium and potassium intake, as well as changes in urine sodium.

Table 1. Study Timeline

	Year 1	Year 2	Year 3
Finalize protocol, develop MOP, and study forms	X		
Training and certification, pilot testing, IRB approval	X		
Recruitment	X	X	X
Intervention and data collection, quality control	X	X	X
Data analysis			X

2. Subject Population

2A. Inclusion Criteria

- Men or women aged >18 years of any race/ethnicity
- Elevated BP or hypertension at screening (untreated office systolic BP 120-159 and diastolic BP <100 mm Hg)
- Willing and able to provide informed consent

2B. Exclusion Criteria

- Medical condition in which potassium supplementation is contraindicated:
 - History of heart failure, myocardial infarction, stroke, or cardiac arrhythmia

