All participants will be age 18 years or older because elevated BP and hypertension are not common in children. There is no upper age limit and we expect the distribution of age of study participants to reflect the age distribution of adults with elevated BP or hypertension in the greater New Orleans, LA metropolitan region, which aligns with the overall goals of the study. The investigators have substantial prior experience carrying out clinical research among adults aged 18 and older. We plan to recruit approximately 50% women participants in the proposed trial. Although there is not strong evidence to suggest sex differences in blood pressure response to potassium supplementation, we will investigate the consistency of treatment effects

by sex in a pre-specified subgroup analysis. We plan to recruit approximately 40% ethnic minorities in the proposed trial. Previous trials suggest there may be racial differences in the effects of potassium supplementation on blood pressure. For example, black adults have shown a larger blood pressure response to supplementation in prior trials. Therefore, we will investigate the consistency of treatment effects by race in a pre-specified subgroup analysis.

3. Procedure

3A. Overview of Trial Design

We will conduct a randomized placebo-controlled double-blind trial testing the intake-response effect of oral potassium supplementation on BP in adults with elevated BP or hypertension (**Figure 1**).

We will recruit 224 adults with elevated BP or hypertension (untreated office systolic BP 120-159 and diastolic BP <100 mm Hg) from the greater New Orleans metropolitan area and randomly assign them to placebo or 1 of 3 intervention arms in which in which 0, 30, 60, or 90 mmol/day (0, 1173, 2346, or 3519 mg/day) of additional potassium is given orally for 12 weeks. We will test the effects of various potassium doses on net 24-hour systolic BP changes from baseline to 12 weeks of follow-up (primary outcome). We will assess safety parameters and additional secondary and exploratory outcomes, including 24-hour diastolic BP, office and nighttime BP, other CVD risk factors, and consistency of effects by subgroups of age, sex, race, baseline BP, central adiposity, and baseline sodium and potassium intake. **Table 2** summarizes the trial components.

Table 2. Study Overview

Study Design	Randomized, double-blind, placebo-controlled, intake-response clinical trial

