Study Participants	224 adults with elevated BP or hypertension (untreated office systolic/diastolic BP 120-159/<100 mm Hg)
Intervention Groups (n=56 per group)	Supplemental oral potassium in 3 arms: 30 mmol/day (1173 mg/day), 60 mmol/day (2346 mg/day), or 90 mmol/day (3519 mg/day) for 12 weeks
Control Group (n=56)	Placebo for 12 weeks
Primary Outcome	Difference in 24-hour systolic BP change from baseline to 12 weeks among the 4 groups
Secondary and other Outcomes	24-hour diastolic BP; office and nighttime BP; sodium excretion; effect mediation and modification by age, sex, race, baseline BP, central adiposity, baseline urine excretion of sodium and potassium, and change in urine sodium

3B. Randomization and Blinding

Eligible participants will be randomly assigned to placebo or 1 of 3 active intervention groups in a 1:1:1:1 ratio using a stratified (Black vs. non-Black) block (random sizes of 4 and 8) randomization scheme generated via computer program and concealed by an independent biostatistician within the Bioinformatics and Biostatistics Core. Randomization is expected to balance baseline characteristics (e.g., dietary intake) among groups. After eligibility is confirmed, clinical staff will ensure all baseline data is in place and checked for quality control purposes and will obtain the participant's randomization assignment via secure web-based database (REDCap). Once participants are randomized, every effort will be made to obtain complete follow-up information.

The proposed trial will employ placebo control and blinding of participants and study staff recording participant information, which are effective measures to account for the possibility of intervention placebo effects. The Bioinformatics and Biostatistics Core will control the randomization and intervention allocation, preserving the blinding of the investigators and Clinical Research and Community Engagement Core study staff in charge of day-to-day operations. Study participants will receive potassium tablets or placebo and will be unaware of their placebo or dosing assignment, and therefore unlikely to differentially change their diet over the course of the trial (i.e., cross-over). 24-hour BP monitoring is resistant to placebo effects and is unlikely to be affected by the possibility of observe unblinding.³³

3C. Intervention and Control

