Questionnaires: A medical history and medications questionnaire will be administered at the first screening visit and updated at weeks 6 and 12 to ascertain conditions requiring changes in therapy. Social and behavioral risk factors will be assessed. Safety questionnaires will be administered at screening and subsequently over the trial to assess safety, potential adverse events, and symptoms classified by frequency and severity. 24-hour dietary recalls will be administered by a trained study dietitian or technician (1 in-person, 1 via telephone).

BP and anthropometric measures: Office BP will be measured 3 times at each study visit, with averages of the 6 measurements at the 2 baseline and 2 12-week visits used to minimize random error. BP measurements will be performed by staff trained and certified in a standardized BP measurement protocol using the same model of validated oscillometric device (Omron HEM-907xl) for each participant at each study visit. Participants will be asked to rest quietly while seated in a chair with an upright back with their feet flat on the ground for five minutes prior to BP measurements. Participants will be instructed to avoid alcohol, coffee, smoking, and exercise 30 minutes prior to BP measurements. An appropriate size cuff will be used over a bare arm for a mid-brachial reading at heart level. The participant's arm will be rested comfortably, and no talking will be permitted before or during the measurement. Calibrated instruments will be used to measure height at the initial screening visit, and weight and waist circumference at each visit.

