Missing Data and Covariable Adjustment: In the primary analyses, we will use Markov-chain Monte Carlo methods to impute missing values assuming an arbitrary missing pattern and a multivariate normal distribution for the data.^{55,56} We will compare point estimates and confidence intervals from this analysis with a secondary analysis using available data without imputation. In this proposed RCT, we expect baseline characteristics to be balanced between intervention groups. Therefore, in the primary analysis, we will include the stratified randomization variable (i.e., race) as a covariable, but other covariable adjustments will not be used. However, if imbalances are detected, we will adjust for these covariables in secondary multivariable-adjusted regression models.

Analyses of Effect Modification and Mediation: We will evaluate the consistency of intervention effects by age, sex, race, baseline BP, central adiposity, and baseline sodium and potassium intake in stratified analyses. Effect modification will be tested using intervention arm * subgroup interaction terms in regression models. Mediation analysis will be used to evaluate potential mechanisms of potassium supplementation on outcomes. We will compare changes in covariables that could be impacted by the intervention, such as urinary excretion of sodium and potassium, and use structural equation modelling (SEM). SEM allows for simultaneously modelling both indirect and direct effects; i.e., effects of the intervention on the mediator, effects of the mediator on the outcome, as well as the direct effects of the intervention on the outcome (e.g., systolic BP).⁵⁷

The proposed trial is designed to test one primary hypothesis and the other analyses will be considered hypothesis generating. Therefore, a significance level of 0.05 without adjustment for multiple comparisons will be used in analyses of secondary outcomes, subgroups, and effect mediation and modification.

4. Risks

4A. Description of Potential Risks

Risks associated with potassium supplementation, venipuncture, and collection of confidential medical information are the main risks associated with this study.

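### Five of the seven planned effect modifiers are continuous but would be tested as unspecified subgroups; if modification is roughly linear, this costs power and makes the result depend on the cut

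*Combined protocol and SAP*

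**What the plan says.** The exploratory hypotheses in the opening section state that "we will explore treatment effects by subgroups, including age, sex, race, baseline BP, central adiposity, and baseline sodium and potassium intake". Section 3I (Analyses of Effect Modification and Mediation) says consistency will be examined "by age, sex, race, baseline BP, central adiposity, and baseline sodium and potassium intake in stratified analyses", and then: "Effect modification will be tested using intervention arm * subgroup interaction terms in regression models". It describes no other test of effect modification. It does not say how many groups each factor will have, where the cuts fall, or whether any factor will enter as a continuous variable.

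On how the factors are measured:

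- **Age:** section 2 says "There is no upper age limit", so age spans the adult range.
- **Baseline BP:** the study aims restrict office BP at entry to "average untreated office systolic BP 120-159 mm Hg and diastolic BP <100 mm Hg". Ambulatory BP is also measured at baseline, and section 3I does not say which is meant.
- **Central adiposity:** section 3E provides for "weight and waist circumference at each visit". No section says that waist circumference is the adiposity modifier; taking it so is an assumption.
- **Sodium and potassium:** section 3I speaks of intake, while Table 2 lists "baseline urine excretion of sodium and potassium". Both are continuous.

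Section 3I also says that, apart from the one primary hypothesis, "the other analyses will be considered hypothesis generating", and it uses 0.05 without adjustment for them.

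**The concern.** Only sex and race are naturally categorical. To form arm-by-subgroup terms for the other five factors, someone has to cut a continuous measurement into groups. Everyone within a group is then treated alike, and variation in the modifier within groups no longer contributes to the test. The trial is sized for the overall dose slope, so interaction tests start with limited power, and grouping usually reduces it further.

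The second cost is arbitrariness. With five factors, no stated cut-points and unadjusted tests at 0.05, the choice of cut can decide which factors appear to modify the effect. The trial wants to learn whether the effect varies with baseline BP and with baseline sodium and potassium, so the quality of these tests matters even though they are exploratory.

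**Working it through.** **1. The plan's own figure (section 3G).** Inputs: two-sided 0.05, 90% power, SD of change 7 mm Hg, 1.5 mm Hg per 30 mmol/day, contrast −3, −1, 1, 3.

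- Group means 0, −1.5, −3.0, −4.5 give a contrast of |1.5 − 3.0 − 13.5| = 15; the squared coefficients sum to 20.
- n = (1.960 + 1.282)² × 49 × 20 / 15² = 45.8 per group by the normal formula.
- With the noncentral t, power is 0.898 at 46 and 0.905 at 47, so 47 reproduces.
- 47 / 0.85 = 55.3, hence 56 per group and 224 in total. Evaluable: 4 × 47 = 188.

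The documents give no figure for the interaction tests, so the rest uses stated assumptions.

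**2. Information kept after grouping.** If modification is linear in the modifier, the share of information kept is the between-group share of the modifier's variance. For a two-group cut of a normal modifier at quantile p, with q the corresponding normal deviate, this is φ(q)² / [p(1 − p)]. At the median it equals 2/π = 0.637.

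| Grouping | Modifier distribution | Information lost |
|---|---|---|
| Median split | Normal | 36.3% |
| 30/70 split | Normal | 42.4% |
| 20/80 split | Normal | 51.0% |
| Tertiles | Normal | 20.7% |
| Quartiles | Normal | 13.9% (14.4% with equally spaced scores) |
| Median split | Uniform | 25.0% |
| Median split | Skewed (gamma, shape 4; lognormal, sigma 0.4) | 41% to 44% |
| Median split | Office systolic BP truncated to 120–159 | 27% to 34% |

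The last row assumes normal parent distributions with mean 138 and SD 20 (27%), mean 133 and SD 12 (32%), or mean 130 and SD 10 (34%). The relative loss is the same whether dose is coded as a trend or as four arms.

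**3. What this does to power.** Code dose in units of 30 mmol/day as −1.5, −0.5, 0.5, 1.5; its variance is (2.25 + 0.25 + 0.25 + 2.25)/4 = 1.25. With a standardized modifier, the SE of the interaction is 7 / √(188 × 1.25) = 0.457. Assume the slope changes by 1.0 mm Hg per 30 mmol/day per SD of the modifier. The noncentrality is then (1.0/0.457)² = 4.80, multiplied by the share kept after grouping: 3.05 for a median split, 3.80 for tertiles, 4.13 for quartiles. Noncentral F power, 180 denominator df, groups unordered:

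| Modifier coding | Dose as trend | Four separate arms |
|---|---|---|
| Continuous | 59% | 42% |
| Two groups (median) | 41% | 27% |
| Tertiles | 39% | 25% |
| Quartiles | 36% | 22% |

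More groups keep more information, but unordered categories spend extra degrees of freedom, which cancels the gain. Scoring the groups in order recovers part of it: 49% for tertiles and 52% for quartiles, with dose as a trend.

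At an assumed 1.5 mm Hg per SD, continuous against median split is 90% against 74% (trend) or 79% against 57% (four arms).

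A simulation of 4,000 trials at 1.0 mm Hg per SD (dose as trend) gave 58% continuous, 41% median split and 49% ordered tertiles. The analytic 59% is therefore slightly optimistic, but the gap stands.

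**The case against.** The strongest reply has four parts.

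- **The plan never says two groups.** A reader might infer that it discards at least 36% of the information. The documents do not support that as a floor. It is the minimum only for two-group cuts of a normal modifier with linear modification. Ordered tertiles or quartiles lose less, and so does a median split of office systolic BP truncated by eligibility. This part stands. It does not restore much power unless the groups are scored in order, which section 3I does not mention.
- **Linearity is assumed.** If the effect steps exactly at the median, the two-group term is the efficient one, and a linear term keeps only 64% of the information. This stands as a real limit: continuous coding is not better in every case. The plan, however, proposes no threshold in any modifier.
- **The assumed modification has no source in the documents, and it is large.** Against the planned slope of 1.5 mm Hg, 1.0 per SD means slopes of 0.5 and 2.5 at one SD below and above the mean; 1.5 per SD means no effect at one SD below and double the effect at one SD above. The power figures illustrate the size of the loss and do not predict what the trial will see.
- **These analyses are exploratory.** A reader might infer that the trial's main conclusion is weakened. It is not: the primary contrast and the sample size do not involve the subgroups. The exploratory label bears on multiplicity and on how strongly results are read; it gives no reason to prefer a less efficient test or leave the cuts open.

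**Conclusion.** The point holds in conditional form. Section 3I commits to stratified analyses and subgroup interaction terms for five continuous modifiers, without cut-points or a number of groups. If modification is roughly linear, the information lost runs from about 14% (ordered quartiles) through 21% (ordered tertiles) to 36% (median split) for a roughly normal modifier. It is about 27–34% for a median split of truncated office systolic BP, and higher for uneven two-group cuts. At an assumed 1.0 mm Hg per 30 mmol/day per SD, with 188 evaluable and SD 7, power falls from about 59% to 36–41% with two to four unordered groups and dose as a trend. The result would also depend on the cuts chosen. No single figure for the loss can be attached to the plan, because the plan does not fix the grouping. The matter is minor: it is confined to exploratory analyses and leaves the primary test untouched.

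**What to change.** Amend the effect-modification paragraph of section 3I along these lines:

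*Effect modification by age, baseline BP, central adiposity, baseline sodium and baseline potassium will be tested with a dose-by-modifier interaction, the modifier entering as a continuous variable. The dose effect will be reported at the 25th, 50th and 75th percentiles of each modifier with 95% confidence intervals. Estimates within strata, at cut-points fixed before unblinding, will be shown for display only. Sex and race (Black, non-Black) will be analysed as categories.*

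The same paragraph should name the measure that represents central adiposity. It would help to do the same for baseline BP (office or ambulatory) and to confirm that sodium and potassium mean urinary excretion, as in Table 2.

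The cost is a few sentences of the analysis plan, with the same data and no change to the primary analysis. The downside is the linearity assumption: the test would be less efficient for a step at a cut-point. The displayed strata let readers check for that.

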Throughout the entire investigation, strict quality assurance (QA) and quality control (QC) measures will be used. This section describes some of the approaches.

Manual of Procedures: We will develop a study protocol and detailed manual of procedures (MOP) that identifies and details standard procedures for all elements of data collection in the trial. The MOP will be adapted from MOPs used successfully in previous RCTs conducted within the Office of Health Research

Training and Certification: Office of Health Research personnel will be trained based on established and effective methods. Training will focus on core trial elements, such as recruitment, retention, intervention, blinding, and data completeness and quality. Periodic re-training/certification sessions will be conducted to ensure all trial-related procedures are being applied in a standard manner across all participants. Throughout the trial, the investigators will monitor every aspect of study performance throughout the trial to make sure that the objectives are met, that study visits are timely and comprehensive, and that data are complete and of high quality. The accuracy of all laboratory measures, particularly crucial exposure, outcome, and intervention monitoring variables, will be carefully scrutinized.

3G. Statistical Design and Power

The trial is designed to detect a 1.5 mm Hg reduction in 24-hour systolic BP for each additional 30 mmol/day supplemental potassium compared with placebo, assuming 60 mmol/day achieves a 3 mm Hg reduction based on meta-analyses.^{25–29,34,35,49} We calculated our sample size assuming: 90% statistical power; a 2-sided significance level of 0.05; and a standard deviation of 7 mm Hg in 24-hour systolic BP change based on prior BP RCT experience in this population.^{50,51} The sample size calculation assumes analysis using a 4-group dose-response contrast test and the estimated sample size for each group based on these assumptions is 47. To allow for an 85% follow-up rate, we will recruit 56 trial participants in each group for a total of 224.

3H. Data Management

All study data will be double-entered. The study coordinator will conduct quality control checks on all study forms, study measures, and laboratory data. Data will be cleaned and logically checked and entered into a secure REDCap database.

3I. Statistical Analysis Plan

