Intention-to-treat analyses will be conducted such that the primary and secondary study outcomes will be evaluated among participants according to their randomization assignment at study entry.

Preliminary Data Analysis: Baseline participant characteristics will be summarized as the mean \pm standard deviation or median (interquartile range) for continuous variables and number (%) for categorical variables. Intervention groups will be compared on baseline characteristics to identify possible baseline imbalances.

Analyses of Main Effects: In the analysis of the primary and secondary outcomes, we will test the hypothesis that increasing doses of supplemental potassium result in monotonically greater reductions in levels of outcomes from baseline to 12 weeks follow-up in an intake-response

fashion. To test this hypothesis, we will use linear regression and the F-test of the hypothesis that there is a linear trend in mean net response in outcomes across the 4 randomized groups over 12 weeks. Rejection of the null hypothesis ($\mu_0 = \mu_{30} = \mu_{60} = \mu_{90}$) indicates that there is a significant intake-response relationship (i.e., $\mu_0 \leq \mu_{30} \leq \mu_{60} \leq \mu_{90}$ and $\mu_0 < \mu_{90}$) where the net effects will be calculated as mean changes in outcomes from baseline to 12 weeks follow-up in the potassium supplementation groups minus mean change in outcomes in the placebo group). The linear contrast will be tested using contrast coefficients of -3, -1, 1, 3. This approach is standard for dose-response RCTs.^{52–54} The optimal dose will be defined as that which shows the greatest net decrease in systolic BP over 12 weeks compared with placebo.

Based on a prior meta-analysis, the intake-response shape of potassium supplementation on systolic BP is uncertain.²⁸ The proposed trial is designed to evaluate a linear intake-response effect but will have sufficient power to characterize other possible relationships, including threshold effects, using contrast structures like modified linear, quadratic, exponential, and sigmoid.^{52–54}

In additional analyses, we will use linear mixed effects regression models incorporating follow-up outcome measures at both weeks 6 and 12, and will conduct pairwise comparisons between randomized groups in an exploratory analysis.

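### The effect-modification test is not matched to the one-degree-of-freedom dose trend on which the trial is built; a dose-score interaction would be a cheap improvement (minor)

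*Combined protocol and SAP*

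**What the plan says.** Section 3G sizes the trial on a linear dose-response. "The trial is designed to detect a 1.5 mm Hg reduction in 24-hour systolic BP for each additional 30 mmol/day supplemental potassium", with "90% statistical power", "a 2-sided significance level of 0.05" and "a standard deviation of 7 mm Hg in 24-hour systolic BP change". It assumes a contrast test across the four groups and arrives at 47 evaluable per group, 56 recruited. Section 3I (Analyses of Main Effects) uses the same contrast for the primary test: "The linear contrast will be tested using contrast coefficients of -3, -1, 1, 3". That is one degree of freedom.

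For subgroups, Section 3I (Analyses of Effect Modification and Mediation) says: "We will evaluate the consistency of intervention effects by age, sex, race, baseline BP, central adiposity, and baseline sodium and potassium intake in stratified analyses". The test follows: "Effect modification will be tested using intervention arm * subgroup interaction terms in regression models". The plan does not say whether arm enters as a four-level factor or as a dose score, how many degrees of freedom the test has, or whether the terms are tested jointly. It gives no test of whether the dose slope varies with a modifier, no cut-points for the strata, and no power for interactions. The error rate is "a significance level of 0.05 without adjustment for multiple comparisons will be used in analyses of secondary outcomes, subgroups, and effect mediation and modification", and Section 3I treats everything beyond the primary hypothesis as exploratory.

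**The concern.** The primary effect is one number, the change in 24-hour systolic BP per 30 mmol/day. The matching question for a modifier is whether that slope differs between subgroups. A joint test of arm-by-subgroup terms asks instead whether any between-arm difference varies. It spreads the same signal over three degrees of freedom and does not itself return a slope difference with a confidence interval.

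Two things are at stake. Interaction tests in a trial sized for a main effect already have little power, so an avoidable loss matters, and a non-significant result is easily taken as evidence of consistency. Also, leaving coding and df open across seven listed modifiers, each tested at an unadjusted 0.05, leaves a choice to be made after the data are seen.

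**Working it through.** **Inputs from the documents.** Four arms, 1:1:1:1 (3B). SD of change 7 mm Hg, slope 1.5 mm Hg per 30 mmol/day, two-sided 0.05, 47 evaluable per arm or 188 in total (3G). Contrast c = (-3, -1, 1, 3), with sum of squares 20 (3I). About 50% women (Section 2C), used for a 50/50 split.

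**Assumed, because the documents give none.** The slope difference D between two subgroups, in mm Hg per 30 mmol/day, and the non-linear patterns below.

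**Step 1: the plan's own figure.** Net mean changes are 0, -1.5, -3, -4.5, so the contrast is -3(0) - 1(-1.5) + 1(-3) + 3(-4.5) = -15, and its square is 225.
- Normal approximation: n = (1.960 + 1.282)² × 49 × 20 / 225 = 10.507 × 980 / 225 = 45.8 per group.
- Noncentral F with 1 and 4n - 4 df: power 89.8% at n = 46 and 90.45% at n = 47.
- 47 / 0.85 = 55.3, rounded up to 56.

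The 47 and 56 are reproduced with the 1-df contrast. A 3-df overall test at 47 per group would have 78.6% power for the same effect.

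**Step 2: interaction, linear modification.** The variance of a slope per 30 mmol/day in a subgroup with m per arm is 49/(5m), since the dose steps 0, 1, 2, 3 have sum of squares 5 about their mean. With m = 23.5 in each subgroup:
- variance of the slope difference = (49/5) × (2/23.5) = 0.834, SE = 0.913;
- noncentrality λ = D² / 0.834.

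λ is the same for both tests. Only the numerator df differ (1 or 3; 180 residual df).

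| D | λ | Power, 3 df | Power, 1 df |
|---|---|---|---|
| 0.75 | 0.67 | 9.2% | 12.9% |
| 1.5 | 2.70 | 24.5% | 37.2% |
| 2.0 | 4.80 | 41.6% | 58.6% |
| 3.0 | 10.79 | 78.6% | 90.4% |

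A simulation of 4,000 trials at D = 1.5 gave 24.8% and 37.3%. A 40/60 split lowers each figure by at most about 2 points (at D = 1.5: 23.6% and 36.0%). For 80% power the detectable D is 3.05 with 3 df and 2.57 with 1 df. The required λ is 11.14 against 7.93, a ratio of 1.40, so the 3-df test needs about 40% more participants.

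**Step 3: modification that is not linear.** Let δ be the subgroup difference in mm Hg at 0, 30, 60 and 90 mmol/day, and w = 1/(1/23.5 + 1/23.5) = 11.75. Then λ for 3 df = w × Σ(δ - mean δ)² / 49, and λ for 1 df = w × (Σcδ)² / (20 × 49).

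| Assumed δ | Power, 3 df | Power, 1 df |
|---|---|---|
| 0, 2.25, 3.6, 4.5 (concave) | 25% | 37% |
| 0, 0.75, 2, 4.5 (convex) | 25% | 36% |
| 0, 2.25, 4.5, 4.5 (flat from 60) | 30% | 40% |
| 0, 0, 4.5, 4.5 (step at 60) | 42% | 50% |
| 0, 4.5, 4.5, 4.5 (same at all active doses) | 32% | 31% |
| 0, 0, 0, 4.5 (top dose only) | 32% | 31% |
| 0, 2.25, 4.5, 2.25 (peak at 60) | 22% | 17% |

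The 1-df test wins in four of the six monotone patterns and is level in the other two. It loses for the peaked one.

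**The case against.** The case for leaving the plan alone has real force. A joint arm-by-subgroup test is conventional and valid. Section 3I itself calls the shape of the intake-response uncertain and plans threshold, quadratic and sigmoid contrasts, so a test that does not commit to linearity is defensible. The analyses are declared exploratory. No interaction size is given, and for small interactions the gain is slight: about 4 points at D = 0.75 and 2 at D = 0.5 (8.5% against 6.8%). D = 1.5 is already as large as the whole design effect. All of this stands and keeps the point minor. It does not remove it, because the primary hypothesis is itself monotone, most monotone patterns favour the 1-df test, and the fix retains the 3-df test for the rest.

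A reader might infer more than the documents support:
- **That the plan specifies a 3-df test.** It does not. That is the natural reading, but a trend-coded arm is not excluded.
- **That the stated test is the least sensitive available.** Step 3 shows patterns where it is equal or better.
- **That age, baseline BP, adiposity, sodium and potassium will be categorised in the test.** Stratified analyses are planned, but nothing says the interaction test uses cut modifiers.
- **That the protocol predicts a larger response in Black adults.** Section 2C says that earlier trials suggest there may be racial differences, gives a larger response in Black adults as an example, and commits only to examining consistency. Its 40% refers to ethnic minorities, not to the Black versus non-Black stratum of 3B, so the 40/60 figures are illustrative for that factor.
- **That slope differences could not be obtained.** Stratified analyses could yield them, although the plan does not say that they will be reported.

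**Conclusion.** The point holds as a minor improvement. The effect-modification test, as most naturally read, is not aligned with the 1-df dose trend used to size and analyse the trial. Under linear modification at D = 1.5 the mismatch costs about 13 points (24.5% against 37.2%), a third of the power available. The cost is about 4 points at D = 0.75 and 12 at D = 3.0. These figures assume 188 evaluable, SD 7 mm Hg, a 50/50 binary modifier and a joint 3-df test. With all 224 analysed, the figures at D = 1.5 are 29% and 43%.

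Power remains low whichever test is used, so a null interaction will not demonstrate consistency. The sample size, the primary test and the primary conclusion are not affected.

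**What to change.** Amend Section 3I before analysis so that:
- the main effect-modification test for each modifier is the 1-df interaction of the dose score (-3, -1, 1, 3) with that modifier, with arm kept as a four-level factor in the main effects and race included as in the primary model;
- age, baseline BP, waist circumference, and sodium and potassium intake stay continuous in that test;
- the difference in slope per 30 mmol/day is reported with its 95% CI (one 30 mmol/day step is two units of the score, so the coefficient is doubled), per stated unit for a continuous modifier;
- stratified slopes are shown for display;
- the joint 3-df arm-by-subgroup test is retained as supportive.

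It would help to add that power is low: 37% at most for a slope difference of 1.5 or less in a binary modifier, with 188 evaluable.

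The cost is a sentence or two of text, with no new data and no change in sample size. The downside is lower sensitivity to modification that is not monotone in dose, which the retained 3-df test covers. Keeping modifiers continuous also assumes that the slope changes linearly with the modifier, which the stratified display lets the reader check.
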